Hypothesis 4. Progression of disease: Markers of disease progression are lacking in ATTR CA. We hypothesize that attainment of a hierarchical composite endpoint at 1-year of death, heart failure hospitalization, and 30% decline in 6-minute hall walk will be higher in ATTRm vs. ATTRwt CA. In addition, we will explore the capacity of specific markers to assess disease progression including: (1) established circulating biomarkers such as troponin I/T, NT-proBNP, BNP and Galectin-3, (2) novel biomarkers such as RBP4 and TTR concentration, (3) ECG, and

echocardiographic measures including longitudinal strain and MCF, (4) functional capacity by 6-minute hall walk and SPPB, and (5) QOL. Our preliminary data and published work⁹ suggests reduced median survival for ATTRm Val122Ile CA (25 months) vs ATTRwt (43 months) in different race cohorts. We hypothesize that we will observe reduced survival and greater functional decline in ATTR Val122Ile vs ATTRwt within race cohorts.

Hypothesis 5. Performance of risk calculator: Our point-of-care risk calculation utilizing RBP4 and TTR concentration with echocardiographic and ECG determined parameters will be tested in this cohort. We will re-derive the prediction model based upon clinical variables noted above. We anticipate showing a similar degree of accuracy (ROC AUC > 0.95) for identification of cases with ATTR vs. controls

Specific Aim 2: To demonstrate that circulating RBP4 concentration is integral to TTR tetramer stability, which in turn determines the clinical characteristics of ATTR CA. We will measure TTR tetramer stability and RBP4 concentration in serum and urine collected in Aim 1. The overall hypotheses of this Aim are that measurements of TTR kinetic stability, RBP4 and TTR concentration will differentiate patients with ATTR CA vs. non-amyloid HF controls and associate with disease progression and outcomes. Specific hypotheses are as follows:

Hypothesis 1: TTR kinetic stability and RBP4 concentration: We hypothesize that at baseline, TTR kinetic stability will be lower in ATTR CA vs. non-amyloid HFpEF, and that stability will be inversely proportional to plasma RBP4 concentration. We further hypothesize that TTR kinetic stability will be lower for ATTRm vs. ATTRwt.

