Hypothesis 2: TTR kinetic stability and disease progression: We hypothesize that TTR stability will associate with the specific outcomes of survival and disease progression detailed in Aim 1, sub-aim 4. We will explore further TTR stability among patients with indeterminate grade 1 cardiac amyloid scintigraphy scan results (early disease), and hypothesize that stability will be lower than non-amyloid HF controls.

Hypothesis 3: Urinary RBP4 concentrations: We hypothesize that RBP4 will be lower in plasma and higher in urine indexed for renal function by urinary creatinine, and vitamin A concentration, among patients with ATTR CA vs. non-amyloid controls. Reduced RBP4 binding, owing to TTR kinetic instability in blood, will result in increased clearance (and higher urine levels) of the protein. We will also explore RBP4 concentrations among patients with indeterminate grade 1 cardiac amyloid scintigraphy scan results, and hypothesize that serum RBP4 will be lower and urinary RBP4 higher than non-amyloid HF controls.

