2.1.7 Statistical Considerations and Sample Size

Power and Sample Size: The total enrollment proposed for this study is of 800 subjects: 600 Blacks and 200 Hispanics. Amongst them, we expect approximately 80-160 ATTR CA subjects and 640-720 non-amyloid controls. The sample size planned for each race/ethnicity group achieves 80% power to

detect, as in Aim 1: (1) a prevalence of ATTR-CA of 10-15%, (2) a two-fold difference in the prevalence of ATTRm between Blacks and Hispanics (i.e., 0.08 vs 0.04, respectively), as well as, a similar difference in the prevalence of ATTRwt between Blacks and Hispanics, (3) a difference as small as 0.03 (if one truly exists) in the prevalence of ATTRwt with respect to gender (male) distribution between the two race/ethnic groups, and (4) in the ATTR CA group alone, we plan to measure the hierarchical composite endpoint of death, heart failure hospitalization, and 30% decline in 6-minute hall walk after 1 year. A two-sided logrank test with an overall sample size of 80 subjects (40 in the ATTRwt and 40 in the ATTRm) achieves 82% power at a 0.05 significance level to detect a hazard ratio (HR) of 0.44 when the proportion of patients that did not progress in the mutant group is 0.60. This corresponds to a minimum difference of 15% in the probability of not having progressed past 12 months between the two groups.

Aim 2 focuses on comparing differences in TTR kinetic stability and RBP4 concentration between ATTR CA (N=80-120) and the non-amyloid group (N=680-720). These sample sizes generate >95% power to detect: Hypothesis 1) a minimum difference in RBP4 of 5, assuming SDs of 9 and 20 for ATTR CA and non-amyloid, respectively; Hypothesis 2) a mean change difference in TTR stability as small as 0.01, SD of 0.002.

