2.1.8 Data Analysis Plan

Descriptive statistics will be used to summarize subjects' demographics and study outcomes. Sample proportions with exact 95% confidence intervals will be used to estimate the overall prevalence of ATTRm CA in Blacks and Hispanics and by sex. All analyses will be performed in SAS v.9.4 (Cary,NC), at a significance level of 0.05.

AIM 1: Hypotheses 1-3: The differences in proportions for prevalence (#1), genetic mutation status (#2), and sex (#3) will be assessed using Chi-squared/Fisher Exact tests. The genetic ancestry analysis will use 500K SNP data to perform principal components analysis (PCA) and determine the percentage of African admixture in all participants. To identify the associations of rare genetic variants in the TTR gene in ATTR CA cases vs controls, we will utilize burden testing.⁹⁴ **Hypothesis 4:** The main analysis will use the Kaplan-Meier method to estimate the probabilities of the composite endpoint, with medians (95% CI) being reported for each group. Cox regression analysis will be performed to generate the hazard ratio (95% CI), and to allow adjustment for other covariates such as sex or race/ethnicity, or explore interaction with other variables including cardiac biomarkers, echo parameters, or QOL. Alternatively, we will apply and compare Finkelstein-Schoenfeld's unmatched approach⁹⁵ to the matched win ratio,⁹⁶ both methods being used for reporting composite endpoints, with more appropriate priority given to the more clinically important event, e.g. mortality. **Hypothesis 5:** We will test the clinic-based risk calculator that was previously developed and validated in a smaller matched cohort study.⁹⁷ The proposed 4-variable model included: RBP4, LVEF, inter-ventricular septal thickness, mean limb lead QRS voltage, and generated an ROC AUC >90%. This model will be tested in our larger cohort and assessed with respect to prediction capability (AUC ROC) and goodness-of fit (Hosmer-Lemeshow test). We also plan to fit additional multivariable logistic regressions using the variables collected employing variable selection/model-building strategies and comparing the

resulting model(s) to the one proposed above. The variables in the final clinical risk model will be based on weights from the multivariate model.

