AIM 2: Hypothesis 1 and 3: Means (95% CI) and/or medians (inter-quartile range) will be computed for all continuous measurements including RBP4/TTR concentrations. Pearson/Spearman correlation coefficients will be calculated to quantify the strength of the association between RBP4 plasma and urine concentrations in the overall ATTR CA cohort and separately by ATTRm vs. ATTRwt groups. Linear regression models will be used to assess differences in TTR kinetic stability between the two groups, adjusting for RBP4 concentration and vitamin A. **Hypothesis 2:** In addition to descriptive statistics, linear regression models will be employed to test the associations between RBP4 concentration, TTR stability, and cardiac amyloid scintigraphy heart to contralateral chest ratio between the two groups, ATTR CA vs non-amyloid HF controls, adjusting for clinical characteristics and retinol concentration.

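### The analysis labelled Aim 2 Hypothesis 2 contains no outcome variable, so the hypothesised association of TTR stability with survival and progression is not tested as written

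*Combined protocol and SAP*

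**What the plan says.** **Hypothesis.** In section 2.1.6, Aim 2 Hypothesis 2 expects that "TTR stability will associate with the specific outcomes of survival and disease progression detailed in Aim 1, sub-aim 4". It adds an exploratory expectation that stability in grade 1 scans is lower than in non-amyloid controls. The overall Aim 2 statement in the same section expects stability, RBP4 and TTR concentration to separate ATTR CA from "non-amyloid HF controls and associate with disease progression and outcomes". The outcomes referred to are those of Aim 1 Hypothesis 4, which predicts, relative to ATTRwt: "hierarchical composite endpoint at 1-year of death, heart failure hospitalization, and 30% decline in 6-minute hall walk will be higher in ATTRm". It also predicts shorter survival.

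**Analysis labelled Hypothesis 2.** Section 2.1.8 states that "linear regression models will be employed to test the associations between RBP4 concentration, TTR stability, and cardiac amyloid scintigraphy heart to contralateral chest ratio". The contrast is cases against controls, with clinical factors and retinol as covariates.

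**Nearest outcome model.** Under Aim 1 Hypothesis 4, section 2.1.8 plans Kaplan-Meier estimates and a Cox model. The Cox model may be adjusted for sex, race/ethnicity and similar factors. It may also be used to "explore interaction with other variables including cardiac biomarkers, echo parameters, or QOL". Section 2.1.7 fixes the population: "in the ATTR CA group alone, we plan to measure the hierarchical composite endpoint", with ATTRm compared against ATTRwt.

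**Power labelled Hypothesis 2.** Section 2.1.7 claims more than 95% power for a mean change difference in stability of 0.01 with SD 0.002, ATTR CA (80-120) against non-amyloid (680-720).

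**Status.** The synopsis places the association of stability with clinical features and outcomes among the items to be explored (item 5). Section 2.1.1 mentions clinical features only.

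**The concern.** The hypothesis and the analysis that carries its number concern different quantities. A regression among RBP4, stability and the H/CL ratio, by case status, can show whether cases and controls differ in stability. It cannot show whether less stable TTR goes with earlier death or faster decline.

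Section 2.1.5.4 suggests that stabilisation might serve, after validation, as a surrogate biomarker for clinical outcomes. The missing model is the analysis that would bear on that suggestion.

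Treatment handling is also open. Section 1.1.3 describes one approved disease-modifying drug for ATTR-CA, and section 1.4.5 says that this drug stabilises TTR, so it alters the predictor itself. Section 2.2 censors participants who enter investigational trials and leaves access to approved therapy unrestricted, but gives no analysis rule for a participant taking an approved stabiliser.

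**Working it through.** **1. Variables side by side.**

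| | Hypothesis 2 (2.1.6) | Analysis labelled Hypothesis 2 (2.1.8) | Aim 1 Hypothesis 4 Cox model (2.1.8) |
|---|---|---|---|
| Outcome | survival; 12-month composite | none (RBP4, stability, H/CL) | 12-month composite |
| Stability | predictor | one of the related variables | not named |
| Comparison | association with outcome | ATTR CA vs controls | ATTRm vs ATTRwt |

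The list of progression markers under Aim 1 Hypothesis 4 names TTR concentration, not stability. No cell supplies the pairing that Hypothesis 2 needs.

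**2. The plan's own power figure.** Inputs from section 2.1.7: difference 0.01, SD 0.002. Standard error = 0.002 × √(1/n1 + 1/n2).
- 80 vs 720: SE = 0.000236; 0.01/SE ≈ 42; power 1.000.
- 120 vs 680: SE = 0.000198; 0.01/SE ≈ 50; power 1.000.

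The figure reproduces. The difference is 5 SD. At two-sided 0.05, 95% power needs only (1.96 + 1.645) × SE = 0.00085 or 0.00071. None of this concerns outcomes.

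**3. What an outcome model could detect.** The plan gives no effect size for stability on outcome, so this step is illustrative.

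Event rates from section 2.1.7: the event-free proportion in ATTRm is 0.60. With HR 0.44, the proportion in ATTRwt is 0.60^0.44 = 0.799. Events = 0.40 × (ATTRm) + 0.201 × (ATTRwt).

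Two genotype mixes are used: equal groups, and the 56 ATTRm implied by the plan's prevalences (8% of 600 + 4% of 200 = 48 + 8).

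Detectable HR per SD at 80% power, two-sided 0.05 = exp[(1.96 + 0.8416)/√events].

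| ATTR CA | Events, equal / 56 ATTRm | HR per SD, formula | HR per SD, simulation |
|---|---|---|---|
| 80 | 24.1 / 27.2 | 1.77 / 1.71 | 1.85 / 1.78 |
| 120 | 36.1 / 35.3 | 1.59 / 1.60 | 1.64 / 1.65 |
| 160 | 48.1 / 43.3 | 1.50 / 1.53 | 1.53 / 1.56 |

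The simulation used exponential times, a normal predictor and an unadjusted Cox score test. It shows the formula to be slightly optimistic: simulated power at the formula values is 74-77%.

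Sensitivity:
- *The plan's 15-point difference (0.75 vs 0.60) instead of HR 0.44:* 1.69-1.73, 1.57 and 1.47-1.50 by formula.
- *An assumed 30% censored at a random time in the year:* 1.84-1.94, 1.71 and 1.57-1.62 by simulation.
- *Genotype adjustment, assuming genotypes differ by one within-group SD in equal groups:* R² = 0.25/1.25 = 0.2. At N = 80 the formula gives exp[2.8016/√(24.05 × 0.8)] = 1.89.

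**4. Grade 1 scans.** Section 2.2 says that grade 1 is not adjudicated as positive. However, the case rule in section 2.1.5.2 joins visual grade 2 or more and H/CL of 1.3 or more by and/or. A grade 1 scan with a high ratio and SPECT confirmation could therefore be a case, and any grade 1 comparison must say which subjects it includes.

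**The case against.** The strongest reply is that the outcome model already exists. Hypothesis 2 points to Aim 1, whose Cox model has open-ended covariate wording, and stability can be read as one of the biomarkers. Much of this stands: endpoint, method and population can largely be inferred, and trial participants are already censored. It does not close the gap. Stability is never named there, and an exploratory interaction in a genotype comparison does not test a main association. Covariates and stabiliser use also remain open.

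The second reply is that the synopsis calls this association exploratory, so absence of power is a weak complaint. That also stands, and it lowers the weight. But section 2.1.6 states the association as a hypothesis, and section 2.2 speaks of Aim 2 in terms of outcomes.

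A reader might infer more than the documents support:
- *That the power above 95% is wrong.* It is correct for the quantity it names.
- *That the powered change cannot be measured in controls.* Scan-negative non-carriers are followed by phone and have no 12-month sample. This matters only if the change wording is literal, and the opening of the Aim 2 power paragraph favours a plain group comparison.
- *That grade 1 subjects are forgotten.* Section 2.2 commits to exploring their clinical profile and outcomes.
- *That the modelling choices will be made after the data are seen.* They could be; the documents do not show that they will be.

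**Conclusion.** The mismatch is real. As written, the outcome part of Aim 2 Hypothesis 2 has no analysis, and the power item bearing its number applies to something else. This should be fixed, with moderate weight because of the exploratory listing.

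Any outcome model will detect only fairly strong associations when cases are few: about 1.7-1.8 per SD at 80 cases, 1.6 at 120 and 1.5 at 160, by formula and unadjusted. These figures rest on the plan's 0.60 and HR 0.44, the two genotype mixes and complete 12-month follow-up. They do not show any stated figure to be wrong. The finding itself rests on the text and does not depend on them.

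**What to change.** 1. Under Aim 2 Hypothesis 2, add a Cox model of the Aim 1 12-month composite on baseline TTR stability within ATTR CA. Prespecify a short covariate list and report the model with and without genotype.
2. Apply the section 2.2 censoring of trial participants. Add a sensitivity analysis for TTR-stabiliser use, taken from the medication form: use at the baseline sample as a covariate or exclusion, and a later start as a time-dependent covariate or censoring.
3. Keep the existing linear regression for the group comparison. For the grade 1 hypothesis, compare grade 1 subjects who do not meet the section 2.1.5.2 case rule with grade 0 controls.
4. In section 2.1.7, reword the Hypothesis 2 item as a baseline difference between ATTR CA and controls. Either label the outcome model exploratory or state its detectable HR per SD with the assumptions.

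The cost is SAP wording and one further model with its sensitivity analysis, on data already collected. The price is a visibly limited ability to detect modest associations.

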2.2 Limitations and Assumptions

Limited subject recruitment: Our feasibility studies suggest completion of enrollment within the 5-year grant period, leveraging the resources available to us at the various sites. Furthermore, one of our sites (BMC) has already demonstrated recruitment of such a cohort in a currently funded NIH study.

Identification of other types of cardiac amyloidosis: While unlikely, our target population may identify patients with light-chain (AL) amyloidosis. To account for other types of CA, the Co-PIs will scrutinize non-invasive testing data including echocardiography and electrocardiography for all recruited subjects. Any participant with normal TTR genotype but with testing or clinical features suggestive of CA will be referred for further characterization including serum immunofixation electrophoresis and free-light chain assay. Light-chain amyloidosis is unlikely to be identified in this small sample size given a reported incidence of 1:100,000. Subject drop out or unwillingness to complete clinical evaluation for CA: We do not anticipate dropout before the study blood sample is obtained (i.e. immediately after enrollment). Thus, we will be able to perform the TTR genotype analysis and RBP4/TTR measurements as described above. However, a subject might decline to proceed with all clinically recommended testing. Cardiac biopsy is needed to establish the diagnosis of ATTR which occurs in the setting of a monoclonal gammopathy and a diagnostic cardiac amyloid scintigraphy scan, hence some patients may require this as part of clinical care. We anticipate that the number of participants requiring cardiac biopsy will be quite small based upon clinical experience (< 10% of those with positive cardiac amyloid scintigraphy scan)⁷².

common. Among the 110 patients with hypertensive, non-amyloid HFpEF, or HCM, 93% had a grade 0 scan, and 6% had a grade 1 scan. In this application, while we anticipate subjects with grade 1 uptake of CARDIAC AMYLOID SCINTIGRAPHY will be low (<10%), we will explore the significance of a grade 1 scan result in the following ways. First, we will perform SPECT/CT imaging in some subjects with grade 1 myocardial retention of radiotracer to distinguish true myocardial uptake versus blood pool in the LV cavity. Those with the latter (grade 1 scans without myocardial retention of radiotracer but with blood pool in the LV cavity) will represent the false negative population, from which we can calculate the false negative rate. We can also determine if patients with grade 1 radiotracer uptake have a distinct clinical profile by biomarkers, echo, or functional measures and adverse outcomes as we are following patients prospectively in this study. The potential to have false positive with cardiac amyloid nuclear scintigraphy will be addressed by evaluation for AL cardiac amyloid in anyone who has myocardial retention of radiotracer greater or equal to grade 2, as this is the most common cause of a false positive scan. Every such case will be scrutinized and any subjects with normal TTR genotype but with testing or clinical features suggestive of CA will be referred for further characterization as part of routine clinical care for serum immunofixation electrophoresis and free-light chain assay to exclude light chain amyloidosis. While rare (incidence of 1:100,000), light-chain amyloidosis is the most common cause of a false positive scan. Other causes of a false positive nuclear scintigraphy that have been reported in the literature including hydroxychloroquine-mediated cardiotoxicity⁹⁸ and apolipoprotein A-1 amyloid cardiomyopathy⁹⁹ both of which are exceedingly rare and thus unlikely to be seen in our sample. *LVEF criterion:* ATTR CA is typically associated with HFpEF (LVEF>40%), but some patients with advanced disease can have moderate depressed systolic function. Notably, data is emerging that subjects with the Val122Ile variant more often present with a reduced EF. In order not to exclude this important cohort which is a focus of our efforts, we will enroll subjects with an EF >=30%. This may result in recruitment of controls with reduced EF, but we predict that exclusion of ischemic/valvular heart disease as the cause of HF will limit low EF control numbers. *Why is African ancestry not an inclusion criterion?* Given the association of the Val122Ile mutation with African ancestry, use as an inclusion criterion would enhance the identification of subjects. However, the strength of the association of Val122Ile with African ancestry is unknown. Additionally, requirement of African ancestry by genetic analysis would complicate enrollment. We will quantify ancestry¹⁰⁰ to determine its contribution to the observed phenotypes. *Will the Aim 2 on outcomes be confounded by participation in future clinical trials?* We will censor data on subjects enrolled in investigational trials in the longitudinal portion of the SCAN-MP study. If approved by FDA, we will not restrict access of eligible patients to any therapy that could be of clinical benefit. *Early vs. advanced disease:* We needed to choose between selecting a cohort with sufficient chance of identifying enough subjects with ATTR CA (those with HF) versus identification of subjects with early disease. Our active ascertainment of cases and use of Tc99-PYP or Tc99-HMDP, which identifies ATTR CA prior to echocardiographic changes^{101, 102} coupled with inclusion of subjects with mild forms of HF, should ensure identification of subjects with earlier disease than current practice. *Reduced RBP4 expression/Vitamin A confounding:* We are not able, in this design, to specifically determine the expression of RBP4 as this would require liver biopsy and quantitative PCR. However, data suggest that RBP concentrations vary not by expression but rather by clearance³⁸, as we have postulated. Furthermore, we are measuring

serum vitamin A, and urinary creatinine, as a means to correct for confounding factors. *Unequal percentage of subjects with insulin resistance between groups*: As serum RBP4 concentration is increased in insulin resistance, to control for the potential confounder of unequal distribution of insulin resistance across our subject groups, we will adjust the analysis by history of diabetes and serum glucose. Our preliminary data has shown that glycated hemoglobin or lipids levels do not significantly interact with RBP4 concentrations in the target HFP EF population .

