1.1.3 Pathogenesis and Outcome

Cardiomyopathy in ATTR (ATTR-CA) occurs when insoluble TTR amyloid fibrils deposit in cardiac tissue causing heart wall thickening with diastolic and systolic dysfunction, conduction defects, and arrhythmias, leading to congestive heart failure and death.

While there is a paucity of longitudinal clinical data on ATTR-CA, a few published reports have shown that ATTR patients have a significantly worse prognosis compared to other causes of heart failure, with rapid deterioration of functional capacity, including their ability to walk as measured by the 6-MWD, and quality of life (QOL) resulting in early mortality.

The median survival of Val122Ile patients from time of diagnosis in two retrospective studies was 27⁷ to 41 months^{7, 8} and in the prospective Transthyretin Amyloidosis Cardiac Study (TRACS) study median survival was 26 months.⁹

There is currently only one approved disease-modifying treatment option specifically for patients with ATTR-CA, Tafamidis Meglumine. Another therapy that has shown efficacy in TTR amyloid polyneuropathy is diflunisal (a non-steroidal anti-inflammatory agent) which when administered at a dose of 250 mg PO twice a day delayed progression of neuropathy when compared to placebo.¹⁰ As ATTR-CA is progressive and many patients are anxious to receive a potentially disease modifying agent, there has been an increasing use of diflunisal in such patients, with a single report of safety over an intermediate time period in an uncontrolled study.¹¹

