1.4.5 A method to quantify TTR kinetic stability

In collaboration with [name] and colleagues at Scripps, we have been studying the structure, energetics and dynamics of WT and mutant TTR in human plasma, towards development of mechanisms to identify individuals susceptible to TTR-CA and predict clinical benefit in treating TTR-CA. Using a published subunit exchange method for quantifying the kinetic stability of human TTR in plasma, we were able to demonstrate that tafamidis kinetically stabilizes TTR and that the extent of TTR kinetic stabilization correlated with the tafamidis plasma concentration.⁸⁰ Additionally, using this simple assay carried under physiological conditions, we were able to optimize the dose of tafamidis in a patient's plasma to maximize TTR kinetic stability.⁸¹ We hypothesize that by studying the kinetic stability of WT TTR in plasma, that we can identify those at risk for developing TTR-CA (see below).

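### Follow-up is censored for trial drugs but not for approved or off-label TTR stabilisers, so the 12-month stability change, Aim 2 hypothesis 2 and Aim 1 hypothesis 4 can mix drug effect with natural history

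*Combined protocol and SAP*

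**What the plan says.** Section 2.2 (Limitations and Assumptions) asks whether outcomes could be confounded by participation in future trials. Its rule is: "We will censor data on subjects enrolled in investigational trials in the longitudinal portion of the SCAN-MP study". For therapy that gains approval it adds that "we will not restrict access of eligible patients to any therapy that could be of clinical benefit". That is a statement about access; it does not say how the resulting data are analysed.

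Section 1.1.3 states: "There is currently only one approved disease-modifying treatment option specifically for patients with ATTR-CA, Tafamidis Meglumine". It also says that "there has been an increasing use of diflunisal in such patients". Section 1.4.5 reports that "tafamidis kinetically stabilizes TTR and that the extent of TTR kinetic stabilization correlated with the tafamidis plasma concentration", found with a subunit exchange method. Section 2.1.5.4 names the same method, with the same citation, as the study's stability assay.

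TTR kinetic stability is measured at baseline and 12 months, and medications are recorded at baseline, 6 and 12 months (Table 4). The Medications form in Appendix 4 has start and stop dates. In 2.1.8, the Cox model for hypothesis 4 gives sex and race/ethnicity as examples of covariates. The Aim 2 models name RBP4, vitamin A or retinol, and clinical characteristics. Stabiliser use does not appear as a covariate, exposure, censoring event or sensitivity analysis. The eligibility criteria do not exclude current or past stabiliser use.

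**The concern.** The plan accepts that drug exposure can confound the longitudinal data, but handles only one route to it. A participant diagnosed by the study scan may start an approved or off-label stabiliser, stay in follow-up and be analysed as if untreated.

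Three analyses are exposed:

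- **12-month change in TTR stability.** A drug started between the two samples acts on the measured quantity itself.
- **Aim 2 hypothesis 2 (stability and outcomes).** A drug that raises stability and may also slow progression can create or distort the association under study.
- **Aim 1 hypothesis 4 (ATTRm against ATTRwt at 1 year).** If one genotype group is treated more, or responds more, part of the genotype contrast is a treatment contrast. Section 1.3.2 already raises poor access to care as a rival explanation for the worse Val122Ile course, so unequal uptake is a plausible worry.

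**Working it through.** **1. Which analyses the gap reaches.**

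- Aim 2 hypothesis 1 is specified at baseline (2.1.6). The baseline checklist in Appendix 4 suggests drawing blood and urine (item 11) before tracer injection (item 12) and the scan (item 15). A participant diagnosed by this study is therefore sampled before diagnosis. Only those already on a stabiliser at entry can affect hypothesis 1, or hypothesis 3 on baseline samples.
- Scan-negative non-carriers are followed by phone (Table 4; 2.1.5.8). The 12-month stability value exists for scan-positive participants and Val122Ile carriers, who are the people likely to be offered a stabiliser.
- Hypothesis 4 and the outcome part of Aim 2 hypothesis 2 use follow-up after diagnosis, so both include treated time.

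**2. The plan's own figure for hypothesis 4.** Section 2.1.7 gives 40 per group, two-sided 0.05, HR 0.44, 0.60 progression-free in the mutant group, and 82% power.

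- ATTRwt progression-free: 0.60^0.44 = 0.799.
- Events: 40 × (1 − 0.60) + 40 × (1 − 0.799) ≈ 24.
- Power: 52% (Schoenfeld), 48% (Freedman), 50% (simulated logrank, 4,000 runs, exponential times).
- 82% power would need 50 (Schoenfeld) to 55 (Freedman) events.

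The stated 82% does not reproduce. That is a separate point; here it means hypothesis 4 has few events to spare.

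**3. No censoring, as now planned.** The documents give no stabiliser uptake, start time or cardiac effect size, so these are assumptions: start at month 3, drug HR h of 0.5 to 0.7, uptake u by group. Ignoring depletion of the risk set, a group's average hazard relative to untreated is

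0.25 + 0.75 × [1 − u(1 − h)]

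| h | u = 75% | u = 25% | ratio, 25% group to 75% group |
|---|---|---|---|
| 0.5 | 0.719 | 0.906 | 1.26 |
| 0.7 | 0.831 | 0.944 | 1.14 |

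Large-sample simulation of the event-rate ratio, ATTRwt to ATTRm, agrees closely:

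| Uptake ATTRm / ATTRwt | True HR 1 appears as | True HR 0.44 appears as |
|---|---|---|
| 75% / 25% | 1.13-1.25 | 0.49-0.55 |
| 25% / 75% | 0.79-0.88 | 0.35-0.39 |
| Equal (25%, 50% or 75%) | not run | 0.43-0.44 |

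With equal uptake the ratio hardly moves, but expected events fall from 24 to 18-23 and power from 50% to 39-47%.

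**4. Censoring at stabiliser start instead.** Start at month 3, equal uptake, HR 0.44. At 50% uptake, for example, expected events are 40 × [0.5 × 0.40 + 0.5 × (1 − 0.60^0.25)] + 40 × [0.5 × 0.201 + 0.5 × (1 − 0.799^0.25)] ≈ 10.4 + 5.1 = 15.5.

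| Uptake | Events | Simulated power |
|---|---|---|
| 25% | about 20 | 42% |
| 50% | about 16 | 32% |
| 75% | about 11 | 24% |

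This simulation makes treatment start independent of prognosis. In practice treatment follows diagnosis and probably severity, so censoring could also be informative.

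**The case against.** The strongest reply is that the plan is open rather than wrong. The Cox covariates are given as examples, interactions with other variables may be explored, and Aim 2 hypothesis 2 adjusts for clinical characteristics. Treatment could be included under any of these. That is fair, but nothing commits to it. Section 2.2 does commit to adjusting for diabetes and glucose, so the plan names confounders it means to handle. Its one explicit drug rule covers trial drugs only.

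A reader might infer that all of Aim 2 is contaminated. The documents do not support that: hypothesis 1 is a baseline comparison with blood listed before the scan, and there is no 12-month sample from scan-negative non-carriers.

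A reader might also scale the 0.01 in section 2.1.7 by the untreated share to get a diluted difference from controls. That does not work. The 0.01 is a difference in mean change, not a gap in levels between groups, and no treated share or degree of restoration is given.

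Nor do the documents show that uptake differs by genotype, or size a drug effect on the hypothesis 4 composite. The progression-arrest figures in section 1.4.1 come with no stated cardiac population, and the reference list shows the source as a polyneuropathy trial. The calculations above are scenarios, not predictions.

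**Conclusion.** The asymmetry stands. Followed as written, section 2.2 leaves on-drug 12-month stability values and treated follow-up time in the longitudinal analyses, although the protocol says the approved drug acts on the measured quantity. The analyses affected are the 12-month stability change, the stability-outcome link in Aim 2 hypothesis 2, and Aim 1 hypothesis 4. Aim 2 hypothesis 1, and hypothesis 3 on baseline samples, are affected only by participants already treated at entry.

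For hypothesis 4, bias requires uptake or effect to differ by genotype. Under the assumed 75%/25% split from month 3 and drug HR 0.5-0.7, unequal treatment alone makes a true HR of 1 look like 1.13-1.25 or 0.79-0.88. With equal uptake and effect the loss is mainly in events. This should be settled in the SAP before analysis; it does not undermine the prevalence aim.

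**What to change.** Using the medication start and stop dates already collected:

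1. **TTR stability analyses.** Base them on off-stabiliser samples, excluding baseline users and on-drug 12-month samples. Repeat on all samples as a sensitivity analysis.
2. **Hypothesis 4 and the Aim 2 hypothesis 2 outcome analysis.** Keep the planned analysis and state that it includes treated time. Add two pre-specified sensitivity analyses: stabiliser use as a time-varying exposure, and censoring at stabiliser start. Censoring follows the rule already set for trial drugs; the time-varying analysis is new.
3. **Reporting.** Give stabiliser uptake and start time by genotype, so readers can judge whether the contrast could be a treatment contrast.

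The cost is SAP wording and coding of the medication records; no visit or treatment decision changes. There will be fewer usable 12-month samples. The censored analysis will have fewer events (about 16 instead of 24 at 50% uptake from month 3) and possibly informative censoring, so it should not be the sole analysis for hypothesis 4.
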